7.1.2.1. Model Checking & Diagnostics

The following list of convergence diagnostics will be applied for each parameter:

- The Monte Carlo Standard Errors (MCSE) should be compared with the standard deviation (SD) of the posterior distribution to ensure that only a fraction of the posterior variability is due to the simulation. The number of samples generated and/or the thinning may be increased to reduce the ratio of the MCSE/SD as deemed necessary.
- The Geweke diagnostic test will be used to assess whether the mean estimates have converged by comparing means from the early and latter part of the Markov chain using a z-score t-test. Large absolute values of the z-score statistic indicate rejection of the null hypothesis of no difference between the mean estimates obtained from the early and latter parts of the chain.
- Trace plots of samples versus the simulation index will be visually inspected to assess some aspects of convergence. The centre of the chain should appear stable with very small fluctuations, i.e., the distribution of points should not change as the chain progresses and the posterior mean and variance are relatively constant.
- Autocorrelation plots will be visually inspected to assess degree of autocorrelation (should decline rapidly and show no oscillation patterns).

7.1.3. Sensitivity and Supportive Analyses

If there are greater than 20% of participants with an important protocol deviation that results in exclusion from the Per Protocol Population, the primary analysis may be repeated using the Per Protocol Population.

Change from baseline in clinic visit trough FEV₁ at Day 84 will also be compared between treatment groups using a Bayesian Repeated Measures analysis with covariates for baseline-by-Day interaction and treatment-by-Day interaction. Day will be fitted as a repeated effect within each participant. All post-baseline scheduled visits will be included in the analysis using Day. Non-informative priors will be used for all modelling parameters. Wherever possible conjugate priors will be utilised. An unstructured covariance matrix will be used to model the within-subject error.

A further sensitivity analysis may be performed where Baseline FEV₁ is replaced with the FEV₁ measured post-bronchodilator and prior to dosing on day of hospital discharge for participants who were hospitalised for their index exacerbation, i.e. who were randomized with a Severe index exacerbation but kept as Baseline FEV₁ for participants who were randomized with a Moderate index exacerbation.

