2.2. Study Design

This is a Phase IIb, multicenter, randomized, stratified (by index COPD exacerbation severity [moderate or severe] and by whether or not the participant is in the PK Subgroup), double-blind (Sponsor Open), placebo-controlled, parallel-group study in participants who present with an acute moderate or severe exacerbation of COPD requiring Standard of Care (SoC).

This study consists of a Screening Period, a 12-Week Treatment Period and a 12-Week Post-Treatment Follow-Up Period. Randomization and the first dose of the double-blind study treatment administration (Visit 2/Day 1) should take place in the morning, as soon as possible following determination of eligibility and completion of the baseline measures, including the EXACT-PRO questionnaire for the day of randomization, and FEV₁ measurement and no later than 48 hours after the start of SoC.

PK Subgroup: Sparse PK sampling will be conducted in a subgroup of participants at selected sites. The PK Subgroup will be identical to the main study in terms of the study population, design, and conduct, with the exception of blood draws (3 per visit on Days 14 and 28) for PK analysis.

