5.2. Baseline Definitions

For all endpoints, the baseline value will be the latest pre-dose assessment with a non-missing value, including those from unscheduled visits. If time is not collected, Day 1 assessments are assumed to be taken prior to first dose and used as baseline.

Post-bronchodilator Baseline FEV₁ is defined as the latest FEV₁ measured prior to the first dose of study treatment and post-bronchodilator.

Pre-bronchodilator Baseline FEV₁ is defined as the latest FEV₁ measured prior to the first dose of study treatment and pre-bronchodilator.

Baseline CAT Total Score is defined as CAT Total Score measured prior to the first dose of study treatment on Day 1.

Baseline SGRQ Total Score is defined as SGRQ Total Score measured prior to the first dose of study treatment on Day 1.

Unless otherwise stated, if baseline data is missing no derivation will be performed and baseline will be set to missing.

A centred baseline will be derived for each participant by subtracting the mean baseline across all participants from each participant's baseline value. The 'centred' baseline may be used instead of Baseline in the statistical analyses to aid convergence.

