7.2.4. Change from hospital discharge in clinic visit trough FEV₁

Change from hospital discharge in clinic visit trough FEV₁ will be derived only for participants who were hospitalised for their index exacerbation and who have been subsequently discharged.

Change from hospital discharge in clinic visit trough FEV₁ measured post-bronchodilator is defined as:

FEV₁ measured prior to dosing and post-bronchodilator on Day X – FEV₁ measured post-bronchodilator and prior to dosing on day of hospital discharge.

Where Day X is 14, 28, 56 and 84.

Change from hospital discharge in clinic visit trough FEV₁ measured pre-bronchodilator is defined as:

FEV₁ measured prior to dosing and pre-bronchodilator on Day X – FEV₁ measured prior to dosing and post-bronchodilator on day of hospital discharge.

Where Day X is 14, 28, 56 and 84.

Note, as per Section 5.1 of the Protocol, if discharge takes place between Day 11 and Day 17 (inclusive), the assessments planned for Day 14 may be completed on the day of discharge. In these cases, for this endpoint only, the FEV₁ assessment will be assigned the hospital discharge assessment and the Day 14 assessment will be missing. Refer to Section 13.2.1.1 for further details.

In addition, if discharge takes place after Day 14, the Day 14 assessment will be missing for this analysis.

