7.2.4.1. Statistical analyses

Change from hospital discharge in clinic visit trough FEV₁ will be analysed using a repeated measures analysis as described in Section 7.1.2 if there are a sufficient number of participants to provide a meaningful analysis, otherwise the data will be summarised.

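### The optional FEV₁ sensitivity analysis gives hospitalised participants an on-treatment baseline, so any drug effect present by discharge is removed in the severe stratum only and the analysis does not check the primary effect

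*SAP*

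**What the plan says.** Section and table numbers are those of the first of the three plan versions in the file. The sensitivity-analysis text at issue stands in all three.

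Section 5.2 fixes the baseline of the primary analysis: "Post-bronchodilator Baseline FEV₁ is defined as the latest FEV₁ measured prior to the first dose of study treatment and post-bronchodilator". Section 2.2 places randomisation and the first dose together on Day 1, "no later than 48 hours after the start of SoC".

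Section 7.1.3 then adds an option: "A further sensitivity analysis may be performed" in which "Baseline FEV₁ is replaced with the FEV₁ measured post-bronchodilator and prior to dosing on day of hospital discharge". This applies to those "who were hospitalised for their index exacerbation, i.e. who were randomized with a Severe index exacerbation". For the others the value is "kept as Baseline FEV₁ for participants who were randomized with a Moderate index exacerbation". The section does not say which model is refitted or what the result is meant to estimate.

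The plan expects discharge to fall during treatment. Section 7.2.4 has a rule for discharge on Days 11 to 17 and adds that "if discharge takes place after Day 14, the Day 14 assessment will be missing for this analysis". Section 2.1 lists change from baseline in FEV₁ at hospital discharge among the secondary endpoints.

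Change from discharge is also a secondary endpoint in its own right. Under 7.2.4.1, "Change from hospital discharge in clinic visit trough FEV₁ will be analysed using a repeated measures analysis" if enough participants contribute.

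**The concern.** In 7.1.3 the discharge reading is taken before that day's dose, not before the first dose. A participant discharged several days into the trial has already been taking study drug, so the reading is an outcome of randomised treatment; section 2.1 itself treats it as one. Using it as a baseline subtracts from the Day 84 effect whatever the drug had achieved by discharge.

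The subtraction happens in one stratum only. Moderate participants contribute the full Day 84 effect, and severe participants contribute the part gained after discharge. A pooled estimate averages the two.

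What is at stake is interpretation. If this analysis gave a smaller effect than the primary one, a reader could not tell whether the acute pre-dose baseline had mattered or whether the substitution had removed real early benefit. Telling these apart is the only reason to run it.

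**Working it through.** The plan gives no figure on this point, so there is none to reproduce. The size can only be illustrated.

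**Notation and inputs**
- D, true Day 84 difference from placebo: 75 mL. This is a reporting threshold in 7.1.2, used here as an example and not as a stated design effect.
- p, severe share: 50/170 = 29.4%, the Interim Analysis 1 target in section 3.1. The plan says this proportion may be changed.
- f, fraction of D already present at discharge: not in the documents, so varied from 0 to 1.
- β, slope of Day 84 FEV₁ on the substituted baseline: not in the documents. β = 1 corresponds to a plain change score. With an assumed between-subject SD of 450 mL and visit SD of 150 mL, β = 450²/(450² + 150²) = 202,500/225,000 = 0.90.

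**Formulas**
- Severe stratum: D × (1 − fβ)
- Moderate stratum: D
- Pooled: D × (1 − p × fβ)

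**Example, f = 0.5, β = 1:** severe 75 × (1 − 0.5) = 37.5 mL; pooled 75 × (1 − 0.294 × 0.5) = 64.0 mL.

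**Example, f = 0.5, β = 0.90:** severe 75 × (1 − 0.45) = 41.25 mL. A simulation of a linear baseline-adjusted model in 1,000,000 participants, with the SDs above, gave 41.5 mL.

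| f | Severe, β = 1 | Pooled, β = 1 | Severe, adjusted (simulated) | Pooled, adjusted (simulated) |
|---|---|---|---|---|
| 0 | 75 | 75 | 75 | 75 |
| 0.25 | 56 | 69.5 | 58 | 70 |
| 0.5 | 38 | 64.0 | 42 | 65 |
| 0.75 | 19 | 58.5 | 25 | 60 |
| 1 | 0 | 52.9 | 7 | 55 |

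All entries are in mL. The moderate stratum stayed at about 75 mL throughout. With the pre-dose baseline kept for everyone, the same simulations returned about 75 mL, pooled and in each stratum, for every f.

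**Wider range of slopes.** With β from 0.7 to 1.0 and f = 0.5, the relative loss is fβ = 35–50% in the severe stratum and (50/170) × fβ = 10.3–14.7% pooled. With f = 1 it is 70–100% and 20.6–29.4%.

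**Other severe share.** If half the participants were severe, the pooled estimate at f = 0.5, β = 1 would be 75 × (1 − 0.25) = 56 mL.

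**The case against.** The case for leaving the text alone has several sound parts.

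- The analysis is optional, and the current display lists contain no table or figure for it. The primary analysis, the futility rules and the planned severity subgroups all use the pre-dose baseline. This stands, and it limits the importance of the point.
- Section 7.1.3 names no model. A reader might infer that the discharge value enters the dose-response curve through its baseline coefficients. That is possible, but the sentence follows the paragraph on the repeated measures model, so the text does not settle it. The argument needs neither reading, because baseline is both part of the change score and a covariate in each model.
- The rules for discharge on Days 11–17 and after Day 14 cover contingencies and do not show the usual length of stay. Early discharge could make f small, and a discharge before the first dose on Day 1 would cause no problem. This stands. However, the substitution is not limited to such cases, and nothing in the plan shows that f is zero.
- An effect that persisted despite the substitution would still be informative. That is true, but a reduced effect would remain uninterpretable.

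A reader might go further and infer that the planned comparison of severe with moderate participants is distorted. The documents do not support that: the analyses in 7.1.4 and Tables 2.15, 2.16 and 2.18 are changes from the pre-dose baseline.

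A reader might also conclude that the change-from-discharge endpoint in 7.2.4 should lose its comparison between arms. It is a listed secondary endpoint under an objective framed against placebo, its restriction to hospitalised and discharged participants is stated openly, and it is not offered as a check on the primary result. Removing the contrast would be a trade-off, not a correction.

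**Conclusion.** The point holds in a limited form. The discharge-day value is normally post-randomisation. Using it as the baseline for severe participants alone removes the early effect times the baseline slope in that stratum, so the pooled result combines two estimands. It is not a robustness check of the primary effect.

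The size is unknown. It depends on f, on the slope and on the severe share. None of these is fixed by the plan, and at f = 0 there is no bias. The 70–100% loss in the severe stratum belongs to the extreme in which the whole Day 84 effect is present at discharge, and should not be read as an expected result. Nor does the point cast doubt on the primary analysis, which keeps the pre-dose baseline. The plan should be changed here, but no stated decision depends on this analysis.

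**What to change.** In 7.1.3, remove the discharge-as-baseline substitution as a sensitivity analysis of the primary endpoint, and keep the pre-dose post-bronchodilator baseline for every participant. For the effect in severe participants, rely on the severe-only Day 84 dose-response model already listed as Table 2.16.

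If the sponsor wants the discharge-referenced result, report it for the severe stratum only. Label it as change after discharge among discharged participants, and do not describe it as a robustness check. Leave the 7.2.4 endpoint and its model in place, with the same label.

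Analysing Day 84 FEV₁ itself with the pre-dose value as covariate would not be a useful substitute. The primary model already contains a baseline term with an effectively flat prior, so moving baseline to the other side only turns a₁ into 1 + a₁ and leaves the treatment effects unchanged.

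The cost is one paragraph of SAP wording and a label, with no new data and no listed display removed. The downside is that one optional analysis is lost or relabelled.

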7.1.4. Subgroup Analyses

A subgroup analysis of change from baseline in clinic visit trough FEV₁ by index exacerbation severity will be performed by fitting separate models to each level of the severity subgroup.

A subgroup analysis of change from baseline in clinic visit trough FEV₁ by index exacerbation severity will also be performed by including a treatment-by-severity-by-Day interaction term in the Bayesian Repeated Measures model.

7.2. Secondary Efficacy Analyses

7.2.1. Rate of exacerbations

Rate of exacerbation is defined as the frequency of exacerbations (subsequent to the index exacerbation) within the specified time period, for example, the 12-Week Treatment Period or the 24-Week Study Period.

The length of time on treatment or in study, depending on the specified time-period, for each participant will be calculated for each endpoint as follows:

Endpoint	Time period	Length of time derivation
Rate of (on-treatment) exacerbations, summarised by: 
 • Moderate/severe exacerbations • Moderate exacerbations • Severe exacerbations • All (mild, moderate and 	12-Week Treatment Period	Time from date of randomisation to date of last dose of study treatment

Endpoint	Time period	Length of time derivation
severe) exacerbations		
Rate of (on-or off-treatment) exacerbations, summarised by: 
 • Moderate/severe exacerbations • All exacerbations 	12-Week Treatment Period	Time from date of randomisation to Day 84 (Visit 6) Visit Date. For participants who withdraw early from the study: Time from date of randomisation to date of study withdrawal
Rate of (off-treatment) exacerbations, summarised by: 
 • Moderate/severe exacerbations • Moderate exacerbations • Severe exacerbations 	12-Week Follow Up Period	Time from date of last dose of study treatment to date of study withdrawal/completion
Rate of (on- and off- treatment) exacerbations, summarised by: 
 • Moderate/severe exacerbations • Moderate exacerbations • Severe exacerbations 	Full 24-Week Study Period	Time from date of randomisation to date of study withdrawal/completion

Refer to Section 13.5 for further details regarding the length of time derivation

7.2.1.1. Statistical analyses

The rate of exacerbations will be analysed using a Bayesian generalized linear model assuming a negative binomial distribution for the underlying exacerbation rate with a log link function. An offset to account for the length of time on treatment or in study, depending on the specified time-period, for each participant (as described above) will be included in the model as \log_e (length of time).

Non-informative priors will be used for all modelling parameters. Wherever possible conjugate priors will be utilised.

The median exacerbation rates for each dose arm per 12 weeks, along with the median ratio in exacerbation rates (nemiralisib/placebo) per 12 weeks for each dose, will be estimated and corresponding 95% HPD credible intervals presented. The probability that the true exacerbation rate ratio is less than 1, in addition to other values appropriately selected based on the data, will be presented.

Based on pharmacological predictions, the 500 mcg and 750 mcg doses are expected to result in similar levels of target inhibition and thus potentially translate to similar clinical benefit, therefore estimates of the exacerbation rates for pooled data from 500 mcg plus 750 mcg will also be presented.

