5.4. Examination of Covariates and Subgroups

5.4.1. Covariates

The list of covariates may be used in descriptive summaries and statistical analyses, some of which may also be used for subgroup analyses. The key covariates of interest are Index exacerbation severity, Smoking history and Region. Additional covariates of clinical interest may also be considered. The decision to include covariates in the model will be based on their impact on the model fit and/or convergence and will be detailed in the CSR.

A centred covariate will be derived for each participant by subtracting the mean covariate across all participants from each participant's covariate value. The 'centred' covariate may be used in place of the covariate in the statistical analyses to aid convergence.

Covariate	Details
Index exacerbation severity	Categorical variable (Moderate or Severe) derived using the stratification variable from the randomisation system.
Age (at screening)	Continuous variable derived as described in Section 13.6.2.1
BMI	Continuous variable derived using Height and Weight variables collected in eCRF: BMI = Weight (kg) / (Height (m)) ²
Gender	Categorical variable (Male or Female), collected in eCRF
Country	Categorical variable
Region	Categorical variable derived using Country as: 
 • Americas: Canada, Mexico, United States • Asia: Australia, Korea • Eastern Europe: Poland, Romania, Russia • Western Europe: France, Germany, Italy, Netherlands, Spain, Sweden, U.K.
Smoking history	Categorical variable (Current or Former), collected in eCRF
Baseline COPD maintenance therapy type	Categorical variable derived depending on data observed. Possible categories of interest are: Monotherapy vs. Dual therapy vs. Triple therapy
Index exacerbation type	Categorical variable: New or Relapse, derived using the question: "Other than the current prescription, for the index exacerbation, has the subject received oral/systemic corticosteroids and/or antibiotics for a COPD exacerbation within the last 7 days?" in the eCRF: New = No Relapse = Yes
Number of exacerbations in the previous 12 months	Categorical variable derived from "Total number of COPD exacerbations in the last 12 months" in the eCRF. Possible categories of interest are: 0 vs. 1 vs. ≥2
Baseline COPD ICS therapy use	Categorical variable (ICS Use or Non-ICS Use) derived from review of concomitant medications

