7.2.1.3. Exploratory analyses

A summary of exacerbation rate by the following groups will be presented and, if feasible, a subgroup analyses may be performed:

- Index exacerbation type (New or Relapse)
- Number of exacerbations in previous 12 months (0, 1 or ≥ 2).

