7.2.2.1. Statistical analyses

Time to next exacerbation will be analysed using a Bayesian Cox proportional hazards model with the “Efron” method for handling ties.

Kaplan-Meier (KM) estimates of the probability of exacerbation will also be presented.

Non-informative priors will be used for all modelling parameters. Wherever possible conjugate priors will be utilised.

The hazard ratio and corresponding 95% HPD credible intervals for each nemiralisib dose versus placebo will be presented. The probability that the true hazard ratio is less than 1, in addition to other values appropriately selected based on the data, will be presented.

Based on pharmacological predictions, the 500 mcg and 750 mcg doses are expected to result in similar levels of target inhibition and thus potentially translate to similar clinical benefit, therefore an estimate of hazard ratio for pooled data from 500 mcg plus 750 mcg nemiralisib doses versus placebo will also be presented.

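### The SAP does not fix exacerbation history as a covariate in the exacerbation models: it is collected and listed, but its inclusion is decided after the data are seen

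*SAP*

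**What the plan says.** For the rate, 7.2.1.1 states: "The rate of exacerbations will be analysed using a Bayesian generalized linear model assuming a negative binomial distribution for the underlying exacerbation rate". It gives a log link and a log-time offset and names no covariate. For time to event, 7.2.2.1 states: "Time to next exacerbation will be analysed using a Bayesian Cox proportional hazards model". It gives the method for ties and names no covariate. Sections 7.2.1.2 and 7.2.2.2 bring in index severity only as a treatment-by-severity term for a subgroup analysis.

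Section 5.4.1 lists exacerbation history among its covariates, taken from the eCRF item "Total number of COPD exacerbations in the last 12 months", with 0, 1 and 2 or more as possible categories. It then says: "The key covariates of interest are Index exacerbation severity, Smoking history and Region". History is not one of these three. Use of the list is optional: "The list of covariates may be used in descriptive summaries and statistical analyses, some of which may also be used for subgroup analyses". The rule for entry is: "The decision to include covariates in the model will be based on their impact on the model fit and/or convergence", and the choice is to be reported in the CSR.

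Within the rate section, history appears only in 7.2.1.3. The text there is "A summary of exacerbation rate by the following groups will be presented and, if feasible, a subgroup analyses may be performed", and the groups include "Number of exacerbations in previous 12 months". Section 2.2 stratifies randomisation by index severity and PK subgroup, not by history.

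**The concern.** For the other main endpoints the SAP commits to adjusting for the baseline value of the same measurement. FEV1 is adjusted for baseline FEV1 (7.1.2, 7.1.3), and CAT and SGRQ have baseline-by-Day terms (7.2.6.3, 7.2.7.3). The exacerbation models have no such commitment, although the corresponding baseline variable is already on the eCRF.

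Two things are at stake. The smaller is precision in the rate model. The larger is that the model behind a decision criterion stays open. Under 3.1.1 and 3.1.1.1, the exacerbation rate is the second futility step, and end-of-trial success on it means more than 80% posterior probability of a rate reduction on 750 mcg. The trial is sponsor-open (2.2), and Clinical Statistics, Clinical Programming and the Respiratory Data Sciences Group are unblinded at the interims (3.1). A covariate set chosen on fit or convergence would therefore be chosen by people who can see the treatment effect.

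**Working it through.** The SAP gives no event rate, dispersion, planned arm size or precision figure for exacerbations, so there is no stated figure to reproduce. All sizes below rest on assumptions.

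**Assumed inputs**
- History mix for 0 / 1 / 2 or more: 35 / 28 / 37%. This is the placeholder split in mock Shell 1 (630, 505 and 675 of 1810).
- Rates relative to no prior exacerbation: from 1 / 1.2 / 1.5 to 1 / 1.7 / 3.0; middle case 1 / 1.5 / 2.0.
- Mean rate μ: 0.2 to 0.6 per 12 weeks. Residual dispersion k: 0.3 to 1.0.
- Arms: 300 placebo and 100 active, the placeholder pattern in mock Shell 35.

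**Formulas for the log rate ratio**, with p_h the share in history group h, μ_h its mean rate, and CV² the squared coefficient of variation of μ_h:
- Unadjusted variance = (1/μ + k_m)(1/n0 + 1/n1), where k_m = (1 + k)(1 + CV²) − 1.
- Adjusted variance = (1/n0 + 1/n1) / Σ p_h μ_h/(1 + k μ_h).
- SD of the shift from chance imbalance = √[CV²(1/n0 + 1/n1)].

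**Worked case: μ = 0.4, k = 1.0, rates 1 / 1.5 / 2.0**
- Mean multiplier: 0.35 + 0.28×1.5 + 0.37×2 = 1.51. Second moment: 0.35 + 0.28×2.25 + 0.37×4 = 2.46. CV² = 2.46/1.51² − 1 = 0.079.
- Unadjusted: k_m = 2×1.079 − 1 = 1.158. Variance = (2.5 + 1.158)×0.01333 = 0.0488, SE 0.221.
- Adjusted: μ_h = 0.265, 0.397, 0.530, so the sum is 0.0733 + 0.0796 + 0.1281 = 0.281. Variance = 0.01333/0.281 = 0.0474, SE 0.218.
- Variance reduction: 2.7%.
- Imbalance SD: √(0.079×0.01333) = 0.032. At 1.96 SD the rate ratio moves by a factor of 1.07.

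**Ranges**
- Over this grid, adjustment cuts the variance by 0.6% to 9.3%.
- A second grid used multipliers of 1.3–1.6 for one and 1.8–3.0 for two or more, μ of 0.25–0.6, k of 0.4–1.2, and two further history mixes. There the unadjusted variance is 1% to 12% larger (1.4% to 10.4% for the mock-shell mix). A typical 4% is about 2% on the SE.
- With 300 v 100, the imbalance SD is 0.020 to 0.051. The 1.96-SD factor is 1.04 to 1.11, against an SE of about 0.16 to 0.29.

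**Simulation of the rate model** (598 usable fits; μ 0.4, k 0.6, 300 v 100, middle multipliers): empirical SD 0.203 unadjusted and 0.202 adjusted, with no bias from leaving history out. The two estimates differed within a trial with SD 0.036.

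**What that difference can do at the criterion.** 0.036/0.203 = 0.18 SE. A posterior probability of exactly 80% corresponds to z = 0.84. Moving by ±0.18 gives Φ(0.66) ≈ 75% or Φ(1.02) ≈ 85% (normal approximation, flat prior). Including or dropping the term can therefore decide a borderline case.

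**Cox model.** Simulated mean SEs of the log hazard ratio, unadjusted then adjusted: 0.2298 and 0.2304 (270 v 90, multipliers 1 / 1.4 / 2.2, rate 0.4, k 0.8); 0.1955 and 0.1961 (270 v 90, 1 / 1.6 / 3.0, rate 0.6, k 0.4); 0.1613 and 0.1616 (270 v 270, first multipliers). Separate runs gave 0.257 v 0.258 and 0.1708 v 0.1712. Adjustment did not narrow the interval in any of them.

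**The case against.** The strongest reply is that the plan does not leave history out. Sections 7.2.1.1 and 7.2.2.1 do not say that treatment and offset are the only terms, 5.4.1 lets any listed covariate in, and a strongly prognostic history is what a fit-based rule would tend to admit. That stands against any claim of omission. It does not answer the objection to a choice made on unblinded data.

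A reader might also infer more than the documents support:
- *That history is used only descriptively.* Section 7.2.1.3 also allows a subgroup analysis if feasible, and 5.4.2 lists history as a subgroup.
- *That imbalance biases the rate ratios.* It is random error and the unadjusted interval already carries it.
- *That small dose arms drive the problem.* No planned arm sizes are given. The futility comparison is 750 mcg v placebo, which the mock shells show at about equal size (300/300, 42/43). At 300 v 300 the imbalance SD falls to 0.014–0.036.
- *That both models lose precision.* The Cox runs show no narrowing.
- *That the futility rule is automatic.* It is described as a guideline, the rate is reached only after FEV1 looks futile, and all data are reviewed before stopping.

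The reply also rightly notes that fixing history alone would leave index severity, the stratification factor, just as open.

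**Conclusion.** The point holds as a gap in prespecification with a modest efficiency cost. The SAP collects and lists the baseline count of the same event, excludes it from the key covariates, and leaves its entry to a decision made on the data. In the rate model, following the plan may forgo about 1% to 12% of the variance of the log rate ratio. That range depends wholly on assumed rates, dispersion and history mix. The sharper consequence is an open modelling choice that can shift a result sitting at 80% posterior probability by about five points either way, in the simulated case. For the Cox model the reasons to prespecify are consistency and protection against chance imbalance, not narrower intervals. Nothing here shows bias in the planned rate ratios or hazard ratios.

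**What to change.** In 7.2.1.1, state in advance that prior-year exacerbation count (0, 1, 2 or more) and index severity are fixed covariates in the negative binomial model at Interim Analysis 2, the End of Treatment Interim Analysis and the final analysis (SAC). Apply this to the pooled 500 + 750 mcg estimate and to the exacerbation futility calculation as well. Report the unadjusted ratio as a supportive row. Amend 5.4.1 so that the fit-or-convergence rule does not override this set.

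In 7.2.2.1, prespecify the same covariates, claim no gain in interval width, and say that the hazard ratio is then conditional on them.

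The cost is SAP wording and model terms, with no new data and no extra participants. The small downside is the changed meaning of the hazard ratio in the Cox model.
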